2.1 Definitions

All subjects with signed informed consent are considered as **enrolled subjects**, even if they did not receive any trial treatment.

All randomised subjects will be included in the **Intention-to-treat (ITT)** populations. This population is the primary analysis population. Within ITT population analyses subjects will be assigned to the treatment to which they were randomised. For the combined analysis the ITT Population consists of all patients that are at least in the START or the STOP block.

The **safety** population comprises all subjects who received at least one dose of trial treatment. In analyses of the safety population subjects will be assigned to the treatment which they actually received.

The analysis populations will be defined prior to unblinding of the study.

2.2 Scope

The primary population for the analyses of efficacy are the ITT Populations (randomised patients) for each block. For the combined analysis the ITT Population consists of all patients that are at least in the START or the STOP block.

Safety parameters will be analysed based on the safety population for the assessment of safety.

2.3 Major Protocol Violations

No per protocol analysis will be done.

3 Study Centres

Recruitment and treatment of subjects is expected to be performed in > 100 trial centres.

4 Analysis Variables

4.1 Demographics and Baseline Characteristics

Demographics

Birth date (not analysed)

Gender

Age (calculated)

Nationality

Baseline Characteristics

Concomitant diseases (in the year before screening / current)

*Physical examination (without finding yes/no, several body systems
normal/abnormal)

*Vital signs (height (cm), weight (kg), heart rate (b/min), blood pressure
systolic (mmHg), blood pressure diastolic (mmHg), BMI (calculated),
temperature, cardiotoxicity, hypoglycaemia)

*O2-Saturation (not done / method, O2-Saturation % on room air, O2-Saturation %
and O2-flow (l/min) on oxygen via nasal cannula or face mask)

O2-Saturation – air challenge (not done for 5 minutes, O2-Saturation %, unable to tolerate RA challenge time to saturation of 80%)
O2-Saturation – on high-flow nasal cannula (O2-Satuation %, Flow air, Flow O2)
O2-Saturation – on non-invasive ventilation (O2-Saturation %, PEEP, PIP, Respiratory rate not done)
O2-Saturation – on invasive ventilation (O2-Saturation %, PEEP, PIP, Respiratory rate not done)
O2- saturation - on HFO (O2-saturation %, frequency FHFO, MAP, Amplitude VTHFO)
O2-saturation – on ECMO (O2-saturation %)

****Standard exercise testing (6min-walk not done/not completed/completed, reason for not done) – distance, oxygen saturation, heart rate, Borg-scale (0=nothing at all, ..., 10=very, very severe (max.) at rest and immediately after exercise), if on oxygen: oxygen supplement and flow rate, if test was discontinued: reason and discontinued after xy seconds)**

***Laboratory parameters (value, value normal/abnormal)**

Pregnancy test (male/female without childbearing potential yes/no, lactation period yes/no, pregnant yes/no, test performed yes/no, if test not done: reason)

ECG

Ophthalmological review (Visual acuity and reading acuity, Central visual field, using an Amsler Chart (preferably red on black) or automated perimetry, Slit lamp examination of the cornea, Stereoscopic slit lamp examination of the retina)

pO2, pcO2 (capillary)

**respiratory rate (b/min)*

**retractions*

**coughing*

**oxygen demand*

Chest x-ray scoring for chILD

Pulmonary hypertension (echo)

**measured at subsequent visits as well. Additionally in ventilated patients: Oxygenation index (OI), Duration (h) of mechanical ventilation, NO(%), ECLS (VV/VA/ECLA/Flow/time since insertion)*

*** measured at subsequent visits as well. Additionally in children >5years: FEV1% predicted (recorded in L), FVC% predicted (Recorded in L), 6 minute walking distance (meter), O2 sat before and after 6MWT, Borg scale*

4.2 Primary Variable

START HCQ block and STOP HCQ block

The primary variable is the response rate measured by the oxygen saturation in room air.

START HCQ block

Relative change from trial day 1, i.e. Visit 2, through day 28, i.e. Visit 3, change from active compound compared to change from placebo

STOP HCQ block

Relative change from trial day 1, i.e. Visit 2, through day 84, i.e. Visit 5: change from active compound compared to change from placebo

A) Non-ventilated patients in room air or on O2-supplement

Oxygen saturation in room air

Assessment:

1) If not on O2:

(after 5 min at rest room air, then measure twice over 1 minute each, at least 1 min apart)

** O2 Sat (mean value)*

* Respiratory rate (mean value)

2) If on O2: BEFORE withdrawal:

(after 5 min at rest with steady state O2 supplement, then measured over 1 minute)

* O2 Flow

* O2 Sat (mean value)

* Respiratory rate

Then withdraw O2:

Steady state O2 Sat in air obtained. Steady state minimum SpO2 should be at least 30 seconds without change. Then measured twice over 1 minute each, at least 1 min apart.

If falls to SpO2<80% place back in oxygen and note as <80%.

* O2 Sat (mean value)

* Respiratory rate (mean value)

B) If on high-flow nasal prongs:

O2-flow and air-flow

C) Ventilated patients:

Oxygenation index (OI)

OI = (FiO2 * MPAW) / PaO2

with

FiO2 = Fraction of inspired oxygen

MPAW = Mean airway pressure (= ((frequency * inspiration time)/60) * ((inspiratory pressure (PIP) – PEEP) + PEEP)))

PaO2 = Partial pressure of oxygen in arterial blood

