a Randomization must occur for logistic reasons as soon as possible after concluding all screening investigations and including the patient into the study. This secures delivery of the study medication in time to any study center.

b Weight (kg) and height (cm) will be measured with shoes and clothes off. Vital signs will be collected after the patient has been at rest for 5 minutes.

c Blood sample should include: Blood count with differential, GOT, GPT, gGT, Creatinine, LDH, Potassium, Creatine kinase, blood glucose. HCQ drug level (2 ml EDTA blood and 2 ml of Serum blood). Labor Manual will be provided.

d Spirometry / Bodyplethysmography will be performed pre-bronchodilator in children age  $\geq$  5 years. (If a child  $\leq$  5 years is already able to perform the listed investigations (spirometry or bodyplethysmography), these should also be performed and documented at the discretion of the investigator) The following lung function parameters will be assessed: FEV1 % predicted (recorded in L), FEV 1 (L), FVC % predicted (recorded in L), FVC (L); MEF 75 (L/s); MEF 50 (L/s); MEF 25 (L/s); TLC (L); ITGV (L); RV (L); R eff (kPa\*s/L); R eff predicted (%). SOP will be provided.

e Measurement of O2-Saturation, respiratory rate and O2 flow (if necessary) in awake patient at rest:

If not on O2: after 5 min at rest, room air, then measure twice over 1 min. each; the measurements have to be at least 1 min. apart; report the stable average value

If on O2:

- BEFORE withdrawal (after 5 min at rest with steady state O2 supplement, measure over 1 minute)
- Then withdraw O2 to obtain steady state O2-Sat. in room air (at least 30 seconds without change). Then measure twice over 1 min. each; the measurements have to be at least 1 min. apart; report the stable average value. If the O2-Sat falls below SpO2<80% place back in oxygen and note as exact value.

Document the time of measurement and state of the patient, usually "awake, at rest". Note: In babies avoid crying, eating, sleeping during measurement. Note: try to schedule patients at similar time of the day.

f Borg-Scale: assessment of dyspnea (0 – 10: 0 = no dyspnea at all, 5 = severe dyspnea, 10 = extremely severe dyspnea)

g Standard exercise testing (6-minute-walk test): SOP will be provided

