##### Oxygenation

As respiratory condition is also dependent on the support given to the patient this needs to be taken into consideration when assessing oxygenation. Therefore parameters to be measured were defined depending on the patient's condition (Table 3.3-1). How to analyse these variables statistically is detailed in section 8.

Tab 3.3-1: Oxygenation - specific measurements used to determine, depending on Patient's condition

Patient's condition	Measured parameters	Assessment
In room air	In room air O2 Saturation (mean value) Respiratory rate (mean value)	After 5 min at rest room air, then measure twice over 1 minute each, at least 1 min apart
On O2-supplement	In room air O2 Saturation (mean value) Respiratory rate (mean value)	Before O2-withdrawal take same parameters, after 5 min withdraw O2 and obtain steady state O2 Sat in air. Steady state minimum SpO2 should be at least 30 seconds without change. Then measure twice, over 1 minute each, at least 1 min apart. If SpO2 falls below 80%, place back on oxygen.
On high-	O2-flow, air-flow	After 5 min stable rest measure twice over 1 minute

flow nasal cannula		each, at least 1 min apart
Ventilated	Oxygenation index	$OI = (FiO_2 * M_{PAW})/PaO_2$ ; with $FiO_2$ = Fraction of inspired oxygen; $M_{PAW}$ = Mean airway pressure (= ((frequency * inspiration time)/60) * ((inspiratory pressure (PIP) – PEEP) + PEEP)) $PaO_2$ = Partial pressure of oxygen in arterial blood

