Oxygenation index (OI)	X	X	X	X	X	X	X	X	X
Duration (h) of mechanical ventilation	X	X	X	X	X	X	X	X	X
NO (%) ^g , ECCL (VVVA/ECCL)Flow/time since insertion	X	X	X	X	X	X	X	X	X

X* Tests must be done before first drug dosing

X** Test can be done facultative, but should be done, if initial pCO₂ has been elevated

X*** Chest x-ray is recommended if clinically indicated e.g. to answer the question if the disease is stable

a Randomization must occur after all inclusion and exclusion criteria are met directly after consent to the study is given and at least 1 week before first dose of HCQ or withdrawal treatment. This is necessary to allow for preparation and shipping of the study medication.

c Blood sample should include: Blood count with differential, GOT, GPT, gGT, Creatinine, LDH, BUN, Creatine kinase, drug level, 3 ml EDTA-blood

d Spirometry will be performed pre-bronchodilator in children age ≥ 5 years. SOP will be provided.

e Measurement of O₂-Saturation, respiratory rate and O₂ flow (if necessary) in awake patient at rest:

If not on O₂: after 5 min at rest, room air, then measure twice over 1 min. each, at least 1 min. apart

If on O₂:

- BEFORE withdrawal (after 5 min at rest with steady state O₂ supplement, then measure over 1 minute)
 - Then withdraw O₂ to obtain steady state O₂-Sat. in room air (at least 30 seconds without change). Then measure twice over 1 min. each, at least 1 min. apart. If falls below SpO₂<80% place back in oxygen and note as <80%.

f Borg-Scale: assessment of dyspnea (0 – 10: 0 = no dyspnea at all, 5 = severe dyspnea, 10 = extremely severe dyspnea)

g Standard exercise testing (6-minute-walk test): SOP will be provided

h Health economics assessment with the use of a special questionnaire which has to be filled out by the parents

i Quality of Life assessment with the use of the questionnaire PedsQL for different age groups

j For ophthalmological review please see Chapter 5.1

k Pregnancy test only has to be performed in girls of childbearing age and only if sexual relations are known or probable. It is at the discretion and responsibility of the attending physician to decide, whether a pregnancy test is necessary or not.

2 Analysis Populations

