4.2.1 Efficacy

The following variables will be investigated:

- Oxygen saturation (O2-sat, in room air) (only absolute, as relative already primary outcome) assessed at every visit (not web/tele feedback)
- Respiratory rate (RR, in room air) (relative and absolute) assessed at every visit and every web/tele feedback
- Retractions (yes/no) assessed at every visit and every web/tele feedback
- Coughing last 24 h (yes/no) assessed at every visit and every web/tele feedback
- Oxygen requirement assessed at every visit and every web/tele feedback
- pO2, pCO2 (capillary, in room air)
- Chest x-ray scoring for chILD assessed at screening and visit 3 (START HCQ Block) and visit 5 (STOP HCQ Block)
- Overall survival
- If > 5y old
 - FEV1 % predicted (recorded in L)
 - FVC % predicted (recorded in L)
 - reference values according to the GLI 2012 lung function regression equations
 - 6 minutes walking distance (meter)
 - O2-saturation before and after 6MWT
 - Borg scale
- If ventilated:
 - Duration (h) of mechanical ventilation
 - NO (%), ECMO yes/no, if yes VA/VV, double lumen vs. single lumen, Flow-rate.

4.2.2 *Safety/Tolerability*

Adverse events, clinical laboratory values (GOT, Creatinine, gGT, blood count, differential, LDH, BNP, steady state drug level), ECG, ophthalmologic review

Adverse events will be documented during the study at each visit (exemption: START HCQ between Visits 1 and 2. However, occurring AEs between those visits are not treatment emergent).

Laboratory data will be assessed at screening, visit 3 and visit 4 in the START HCQ Block and at screening, visit 3, 4 and visit 5 and EDTA additionally at visit 6 in the STOP HCQ Block.

Vital signs (respiratory rate, height, weight, BMI, heart rate, blood pressure (systolic and diastolic), temperature, hypoglycaemia (yes/no), appropriate observation of blood glucose levels (yes/no), cardiotoxicity (yes/no), appropriate ECG (yes/no)) will be assessed at screening, and every following visit (not web/tele feedback).

A physical examination will be done at the same visits.

Symptoms and clinical course of treatment will be documented at the same time points as the physical examination is performed and at telephone contact visit.

4.2.3 *Quality of Life (Peds QL)*

Not applicable.

4.2.4 *Health Economics*

Not applicable.

5 Treatment of Missing Values and Outliers

5.1 *Missing Values*

No substitution of missing values is planned.

5.2 *Outliers*

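### The SAP notes a room-air SpO2 below 80% as a category where the protocol asks for the exact value; if the SAP is followed, response cannot be determined for some children on oxygen

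*SAP*

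**What the plan says.** **Recording rule.** The protocol's footnote e to the trial schedule (printed after the STOP table, serving both blocks) covers a child on oxygen whose saturation falls below 80% once oxygen is withdrawn. It says "place back in oxygen and note as exact value". SAP 4.2 says "If falls to SpO2<80% place back in oxygen and note as <80" (per cent), and the SAP's own schedule footnote e repeats this: "place back in oxygen and note as <80". Protocol Table 3.3-1 does not settle the matter. It says "If SpO2 falls below 80%, place back on oxygen" and is silent on what to write down.

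**Primary quantity.** SAP 4.2 defines it for START as "Relative change from trial day 1, i.e. Visit 2, through day 28, i.e. Visit 3" and for STOP as "Relative change from trial day 1, i.e. Visit 2, through day 84, i.e. Visit 5", active against placebo. SAP 6.6 turns this into a yes/no response. For children in room air or on an oxygen supplement, the only criterion in its table is a rise in room-air SpO2 of at least 5%, with no separate definition for STOP. Protocol Tab 3.8-1 uses a fall of at least 5% for withdrawal, and adds respiratory rate and, for children on oxygen, need for support as further routes to response.

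**Handling of non-numeric entries.** SAP 5.1 says "No substitution of missing values is planned". SAP section 6 treats a value as missing only when the visit took place and nothing was documented. SAP 4.1 lists, for the air challenge, a saturation percentage followed by "unable to tolerate RA challenge time to saturation of 80" (per cent).

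**The concern.** A change between two visits needs two numbers. An entry of <80% is documented, so it is not missing under SAP section 6, but it is not a number either, and the SAP gives no rule for turning it into a responder status. Whoever programs the analysis would have to invent one.

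The children concerned are those on supplemental oxygen who desaturate below 80% off oxygen, and they have much room to improve. At follow-up, <80% is itself a post-randomisation result, so any ad hoc handling could act differently in the two arms. Because SpO2 is the SAP's only criterion for this group, no other component can settle an unclassifiable child.

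**Working it through.** The plan has no figure of its own to reproduce: protocol 8.1 gives a target of 80 without a formal calculation. The check is therefore by bounds.

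**Inputs.** Threshold 5% (SAP 6.6; protocol Tab 3.8-1 for STOP). Recording cut 80% (both documents). Let b be baseline and f follow-up. The relative change is f/b − 1 and the absolute change is f − b. Both readings are run, because the documents do not say plainly whether the responder's 5% is relative or in points. An entry of <80% stands for some value from L up to just under 80. The documents give no floor, so L = 60, 70 and 75 are assumptions.

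**Step 1: the numeric change.** With <80% at both visits, the relative change lies between L/80 − 1 and 80/L − 1:

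- L = 60: −25% to +33.3%
- L = 70: −12.5% to +14.3%
- L = 75: −6.25% to +6.7%

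Every range contains the 5% threshold. With <80% at one visit only, the change is still a range. For example, with baseline <80% and f = 82, it runs from 82/80 − 1 = +2.5% to 82/60 − 1 = +36.7% (L = 60).

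**Step 2: responder status under SAP 6.6 (rise of at least 5%).** With baseline <80%, response is certain once f ≥ 80 × 1.05 = 84.0 (relative) or f ≥ 80 + 5 = 85 (absolute).

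| Baseline | Follow-up | Status |
|---|---|---|
| <80% | <80% | undetermined |
| <80% | 80% to below 84% (absolute: below 85%) | undetermined |
| <80% | 84% or more (absolute: 85% or more) | responder |
| 80% or more | <80% | non-responder |

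The first row would be a certain non-response only if baseline values below about 80/1.05 = 76.2% (relative) or 75% (absolute) could be ruled out. The documents do not allow that.

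**Step 3: STOP under the protocol's definition (fall of at least 5%), SpO2 component only.** With follow-up <80%, the smallest possible fall is to just under 80. A 5% fall is therefore certain if b ≥ 80/0.95 = 84.2 (relative) or b ≥ 85 (absolute). At b = 82 the fall could be as small as 2.4%; at b = 88 it is at least 9.1%. From 80% to below 84.2% (or 85%) the status is undetermined, as it is when both visits read <80%. With baseline <80% and follow-up of 80% or more there was no fall, so the child is not a responder on SpO2.

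**Step 4: what exact values would restore.** The pairs 70→79 (+12.9%), 75→79 (+5.3%, or +4 points) and 79→70 (−11.4%) would all be held as <80% at both visits. With exact values the first is a responder on either reading, the second on the relative reading only, and the third not at all under the SAP table.

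**Step 5: weight of one child.** Taking the planned 80 subjects, an equal split between blocks (protocol 3.2) and 1:1 allocation (protocol 3.5.1), an arm holds about 80/2/2 = 20. One child's classification then moves that arm's response proportion by 1/20, or 5 percentage points.

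**The case against.** The strongest reply is that the SAP does not govern bedside recording. Sites follow the protocol, which asks for the exact value, and protocol section 8 says the SAP is based on the protocol. The SAP's schedule also looks like an older copy: day 168 is Visit 6 there and Visit 8 in the protocol, and it has no-visit columns where the protocol has email or phone visits. Leftover wording is a plausible explanation, and exact values may well be in the database. This stands as a reason not to assert that data were lost. It does not remove the need for a correction, because the SAP governs derivation and its primary-variable section points the analyst to the category.

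Four stronger readings are tempting, and the documents do not support them:

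- A reader might infer that SAP 5.1 drops these children. It covers missing values, and a documented <80% is not missing as SAP section 6 uses the term.
- A reader might infer from the time-to-80% item in SAP 4.1 that no number is held. The same entry lists a saturation percentage first.
- A reader might infer that the primary outcome is lost altogether. The tested endpoint is yes/no (Fisher's exact test and logistic regression), and bounds settle several patterns.
- A reader might extend the problem to all of the sickest children. The rule concerns the air challenge in children on supplemental oxygen; high-flow and ventilated patients are judged on flow or oxygenation index.

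The STOP limit of 84.2% also depends on the protocol's definition. Under the SAP table as written, a fall from 80% or more to <80% is a certain non-response.

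**Conclusion.** The two documents contradict each other on how the primary measurement is recorded, and the SAP has no rule for the entry it prescribes. If the SAP wording is followed, relative and absolute SpO2 change cannot be calculated for a child on supplemental oxygen with <80% at either visit, and responder status is open in the two undetermined rows of the table above. Under the protocol's STOP definition it is open in the patterns listed in step 3.

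The textual conflict is certain. Its effect on the data is not: the eCRF coding and the number of children affected are not given, and the number could be zero. The limits treat SpO2 as continuous. If only whole percentages were stored, <80% would mean at most 79%, and the relative START limit would be 79 × 1.05 = 82.95%. Exact values carry one caveat of their own: because oxygen is restored below 80%, the recorded figure may be the reading at which the challenge stopped and not a steady state.

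**What to change.** 1. In SAP 4.2 and SAP footnote e, replace the <80% instruction with the protocol's exact-value rule, and state that the exact recorded SpO2 is analysed. Say how a reading from a challenge stopped early is treated.
2. Before unblinding, confirm how the eCRF stores these entries and count any held only as <80%.
3. For such entries, count a child as a responder only when the bounds make it certain. Add a best-case/worst-case analysis in each block: undetermined children as responders in one arm and non-responders in the other, then reversed. A single stand-in such as 79% is not enough. It sets every <80% pair to zero change, and in STOP a responder in the protocol's sense is a child who deteriorated, so one fixed value does not lean the same way in both blocks.
4. State whether 5% is relative or absolute, and which responder definition the STOP bounds use.

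The cost is SAP wording, one database check and a short sensitivity table. No new data collection is needed, since the protocol already asks for the exact value.
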